**NCT number: [to be filled after registration]**

**Document date:22/07/2022**

## **Study Protocol and Statistical Analysis Plan**

### **Introduction**

Pole dance (PD) combines aerobic and isometric components, with potential to influence cardiovascular variables. The primary objective of this study was to evaluate the acute blood pressure response after a single PD session in young normotensive women. The hypothesis was that a PD session would promote post-exercise hypotension for systolic blood pressure (SBP), without significant changes in diastolic blood pressure (DBP).

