### **Study Design**

This was an experimental, randomized study with a control session. The sample consisted of 21 women practicing pole dance at an intermediate level. Each participant performed two sessions on different days: one experimental session, which consisted of a 60-minute pole dance class, and one control session, which consisted of 60 minutes of seated rest without physical effort. The order of the sessions was defined randomly to ensure balance and minimize bias.

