### **Procedures**

At the beginning of the study, participants underwent an anamnesis to collect sociodemographic data, lifestyle information, comorbidities, and details related to pole dance practice. Anthropometric measurements, including weight, height, and body mass index, were also recorded. In the experimental session, participants completed a 60-minute pole dance class, which included a 15-minute warm-up with joint mobility and stretching exercises, followed by 10 minutes of strength and resistance training combined with transitions. The next 15 minutes focused on aerial movements using the static pole, while another 15 minutes were dedicated to sequences on the spinning pole. The session concluded with a 5-minute passive stretching period. In the control session, participants remained seated for 60 minutes without performing any physical effort.

Blood pressure and heart rate were measured using a digital sphygmomanometer (Omron HEM-7113) at five time points: before the session, immediately after, and at 15, 30, and 45 minutes post-session. Participants were instructed to avoid caffeine, alcohol, smoking, and vigorous physical activity in the 24 hours prior to data collection. Perceived exertion was assessed at the end of the experimental session using the Borg modified scale (0–10).

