### **Statistical Analysis Plan**

Data analysis was performed using SPSS version 17.0. Descriptive statistics were used to characterize the sample, with continuous variables expressed as mean and standard deviation, and categorical variables expressed as absolute and relative frequencies. Differences in systolic blood pressure, diastolic blood pressure, and heart rate between sessions and across time points were analyzed using repeated measures ANOVA (session  $\times$  time), followed by Bonferroni post-hoc tests. Spearman's correlation coefficient was applied to examine associations between blood pressure, heart rate, and perceived exertion. A significance level of  $p < 0.05$  was adopted for all analyses.

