### **Expected Results**

It was expected that systolic blood pressure would show a significant reduction 45 minutes after the experimental session, while diastolic blood pressure would remain unchanged. Heart rate was anticipated to increase immediately after the pole dance session, followed by a gradual return to baseline values during the recovery period.

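### The plan expects diastolic pressure to stay unchanged, but its only analysis is a difference test, and a non-significant result from that test does not show absence of change.

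*Combined protocol and SAP*

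**What the plan says.** The Introduction states one hypothesis with two parts: post-exercise hypotension for systolic pressure (SBP), and DBP "without significant changes in diastolic blood pressure (DBP". The Expected Results section restates the second part without reference to significance: SBP is expected to fall by 45 minutes, "while diastolic blood pressure would remain unchanged".

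The Statistical Analysis Plan treats all three haemodynamic variables alike: "Differences in systolic blood pressure, diastolic blood pressure, and heart rate between sessions and across time points were analyzed using repeated measures ANOVA", with session and time as factors, "followed by Bonferroni post-hoc tests". A 0.05 significance level "was adopted for all analyses". The number of comparisons in the Bonferroni family is not given.

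On the design: "The sample consisted of 21 women practicing pole dance at an intermediate level" and "Each participant performed two sessions on different days", so each woman is her own control. Measurements are taken "at five time points: before the session, immediately after, and at 15, 30, and 45 minutes post-session".

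The documents give no equivalence margin, no equivalence test, no confidence interval for DBP, no SD, and no justification for 21 participants.

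**The concern.** A difference test can support the statement that DBP changed. When it is not significant, the data may fit no change, or a real change that was measured too imprecisely to detect. The p value does not separate the two. This is true at any sample size.

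The incentive also runs the wrong way. Noisier readings, fewer women or a stricter Bonferroni correction all make a non-significant DBP result more likely, and so make this clause of the hypothesis easier to claim.

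What is at stake is the contrast in the hypothesis. A report that SBP fell and DBP did not could follow from data in which both fell by similar amounts and only one crossed the threshold. No planned analysis compares the SBP response with the DBP response directly.

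**Working it through.** The documents contain no power or precision figure, so there is none to reproduce. The steps below show what a non-significant DBP result could conceal.

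**Inputs from the documents.** n = 21 women, both sessions each (Study Design), giving paired differences with 20 df. Significance level 0.05 (Statistical Analysis Plan), taken as two-sided because sidedness is not stated. Five measurement times (Procedures), four of them after the session.

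**Assumptions.**
- The contrast is the control-corrected DBP change: post minus pre on the pole dance day, less post minus pre on the control day.
- Its SD is 6 to 9 mmHg.
- The Bonferroni family is the four post-session times, so the level is 0.05/4 = 0.0125.
- True changes of 3 and 5 mmHg are used as examples.

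**Step 1. Precision.** SE = SD/√21. The 95% CI half-width is t(0.975, 20) × SE, with t = 2.086.
- SD 6: SE = 1.31, half-width = 2.086 × 1.309 = 2.73 mmHg.
- SD 9: SE = 1.96, half-width = 2.086 × 1.964 = 4.10 mmHg.

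**Step 2. Probability of a non-significant result when DBP truly changes by δ.** This is P(|T| < t_crit), where T is noncentral t with 20 df and noncentrality δ/SE. The critical value is 2.086 at 0.05 and 2.744 at 0.0125. For δ = 3 and SD 6 the noncentrality is 3/1.309 = 2.29; for SD 9 it is 3/1.964 = 1.53.

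| SD (mmHg) | δ = 3, level 0.05 | δ = 3, level 0.0125 | δ = 5, level 0.05 | δ = 5, level 0.0125 |
|---|---|---|---|---|
| 6 | 41% | 65% | 5% | 15% |
| 7 | 54% | 75% | 12% | 30% |
| 8 | 63% | 82% | 22% | 44% |
| 9 | 69% | 86% | 32% | 56% |

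For a fixed true change, moving from 0.05 to 0.0125 raises the chance of a non-significant result in every row.

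**Step 3. What an equivalence rule would do with the same 21 women.** The rule is to conclude no relevant change only if the 90% CI (estimate ± 1.725 × SE) lies inside ±5 mmHg. That margin is an illustration and is not in the documents. Simulated probability of meeting the rule:

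| SD (mmHg) | 90% CI half-width | True change 0 | True change 3 mmHg |
|---|---|---|---|
| 6 | 2.26 | 96% | 43% |
| 7 | 2.63 | 87% | 35% |
| 8 | 3.01 | 74% | 29% |
| 9 | 3.39 | 58% | 24% |

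If the SD is near 6, 21 women could well support an equivalence conclusion at this margin. If it is near 9, the answer would often be inconclusive.

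These figures concern a single contrast. The power of the session-by-time ANOVA for DBP would need the correlation structure across the five times, which the documents do not give.

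**The case against.** **The decision rule is inferred.** A reader might take the plan to say that p ≥ 0.05 confirms the DBP hypothesis. No section says so: the Introduction makes a prediction about significance, and Expected Results states an expectation. This objection stands as to wording. What remains is that the prediction is phrased as a significance criterion, Expected Results turns it into a claim of no change, and no other analysis is offered to support either.

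**The sample size is not the root fault.** A reader might infer that 21 women are too few. The documents do not support that without an SD and a margin, and Step 3 shows that 21 can be enough under some assumptions. The fault is the missing rule for interpreting a null result; a small sample makes it worse.

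**The 3 mmHg example sits awkwardly with a ±5 mmHg margin.** Under that margin a 3 mmHg change is not a relevant one, and the equivalence rule would itself report no relevant change in 24 to 43% of trials. This is fair. The 5 mmHg columns are the relevant ones for a sponsor who adopts that margin, and at 0.05 they are much milder (5 to 32%).

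**The Bonferroni figures rest on an unstated family.** Correcting for all ten pairs of the five times (level 0.005) would raise the 3 mmHg miss rates to 77 to 92%. That family belongs to pairwise time comparisons, whereas the SD here is for a session-by-time contrast, so the four-comparison figures are used.

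**DBP is the accompanying clause.** The directional claim is the SBP fall, and an ordinary difference test is suited to it. This stands, and it limits the severity.

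**Conclusion.** The point holds as one of analysis and interpretation. The plan predicts no change in DBP and provides only a test that cannot establish it. That conclusion is logical and needs no assumed figures.

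Its practical size does depend on assumptions: an SD of 6 to 9 mmHg, a paired contrast in 21 women, and a four-comparison family. On those terms the 95% CI would reach 2.7 to 4.1 mmHg either side of the estimate. A true 3 mmHg change would be non-significant in 41 to 69% of trials at 0.05 and 65 to 86% after correction; for 5 mmHg the ranges are 5 to 32% and 15 to 56%.

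A reader might go further and conclude that the trial's main finding is unsafe. The documents do not support that, because the SBP part of the hypothesis is tested in the ordinary way and is untouched. This should be fixed, but it does not invalidate the trial.

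**What to change.** 1. Report the control-corrected DBP change at 45 minutes with its 95% CI.
2. Word a non-significant DBP result as inconclusive, with the range of changes that the interval allows, and not as evidence that DBP is unchanged.
3. Do not infer that SBP and DBP respond differently because one is significant and the other is not.
4. State the Bonferroni family.
5. Conclude no relevant change only if the 90% CI lies inside a margin justified independently of the data. The Timeline section says the study was completed in 2023 and the analyses finalised, so a margin set now must be labelled post hoc. Items 1 to 3 are the sounder remedy.

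The cost is one interval and some rewording, with no new data or participants. The downside is that the DBP statement may become inconclusive. With a ±5 mmHg margin and a true change of zero, equivalence would be shown about 96% of the time at SD 6 and about 58% at SD 9.

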### **Study Design**

This was an experimental, randomized study with a control session. The sample consisted of 21 women practicing pole dance at an intermediate level. Each participant performed two sessions on different days: one experimental session, which consisted of a 60-minute pole dance class, and one control session, which consisted of 60 minutes of seated rest without physical effort. The order of the sessions was defined randomly to ensure balance and minimize bias.

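### The crossover randomises session order but the session × time ANOVA has no order term; a first-visit effect on the within-visit blood pressure course would cost precision near an 11/10 split and shift the contrast when the split is uneven

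*Combined protocol and SAP*

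**What the plan says.** Study Design describes a two-period crossover. "The sample consisted of 21 women practicing pole dance at an intermediate level", and "Each participant performed two sessions on different days": a pole dance class and a seated control. On allocation it says only that "The order of the sessions was defined randomly to ensure balance and minimize bias". It gives no method of generation, blocking, target ratio or number of women per order.

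Procedures has blood pressure taken "at five time points: before the session, immediately after, and at 15, 30, and 45 minutes post-session". In the Statistical Analysis Plan, differences in SBP, DBP and heart rate "between sessions and across time points were analyzed using repeated measures ANOVA", with session and time as the factors, "followed by Bonferroni post-hoc tests". Period, visit and sequence appear nowhere in the plan.

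The Introduction's hypothesis is a fall in SBP after the class, and Expected Results places that fall at 45 minutes. The contrast of most interest is therefore a change from the pre-session reading, compared between sessions.

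**The concern.** Order is the one thing this trial randomises, and the stated model ignores it. In a two-period crossover, a difference between first and second visits that is unrelated to the session adds to each woman's paired difference, with a sign that depends on her order. Left out of the model, it has two possible consequences. Near balance it sits in the residual, so the error variance is too large and the test loses power. With an uneven split it does not average out, and part of it is read as a session effect.

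The form that could touch the hypothesis is a first-visit effect on the blood pressure change. If the pre-session reading is raised on the first visit only, the later fall looks larger on that visit. With more women taking the class first, the class would appear more hypotensive than it is; with fewer, less so.

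**Working it through.** The documents state no effect size, SD, power or split, so there is no figure of theirs to reproduce.

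**Inputs.** From the documents: n = 21, two sessions in random order, five readings per session, session × time ANOVA, significance level 0.05. Assumed: SD of the paired difference σ = 8 mmHg; period effect π of 1 to 4 mmHg (5 mmHg in the simulation); simple randomisation where split probabilities are used; two-sided tests.

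**Model.** For woman i, let D_i be the pole-dance-minus-control difference in SBP change, with D_i = τ + s_i·π + e_i. Here s_i = +1 if pole dance came first and −1 otherwise, τ is the session effect, and π is the visit 1 minus visit 2 difference in the change.

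**1. Bias given the split.** Without an order term, the error in τ is π × (n₁ − n₂)/21.

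| Split | Share of π that leaks | Bias for π = 4 mmHg |
|---|---|---|
| 11/10 | 1/21 = 4.8% | 0.19 |
| 12/9 | 3/21 = 14.3% | 0.57 |
| 13/8 | 5/21 = 23.8% | 0.95 |
| 14/7 | 7/21 = 33.3% | 1.33 |

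**2. How often each split would arise under simple randomisation.** From Binomial(21, 0.5): P(11/10) = 0.336, P(13/8 or worse) = 0.383, P(14/7 or worse) = 0.189. The expected absolute share is 17.6%, so a 4 mmHg effect gives an average absolute error of 0.176 × 4 = 0.70 mmHg.

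**3. Loss of precision at 11/10.** The residual variance rises from σ² = 64 to about 64 + π²:

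- π = 1: 1/64 = 1.6%
- π = 2: 4/64 = 6.3%
- π = 3: 9/64 = 14.1%, like losing 21 × (1 − 64/73) = 2.6 women
- π = 4: 16/64 = 25%, like losing 21 × (1 − 64/80) = 4.2 women

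**4. Error rates.** A simulation of the paired test (40,000 trials per setting, σ = 8, π = 5) gave an unadjusted type I error of 0.023 at 11/10, 0.052 at 13/8, 0.087 at 14/7 and 0.139 at 15/6. Averaged over all splits under simple randomisation it was about 0.05. With an order term it was 0.049 to 0.051 at each of these splits. At 11/10, power for a 5 mmHg effect was 0.699 unadjusted and 0.776 adjusted.

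**5. Which period effects matter for which contrast.** If the first visit adds a constant c at every reading, the 45-minute change on that visit is (SBP₄₅ + c) − (SBP_pre + c), and c drops out. The interaction and change from baseline are untouched; only the session main effect and the between-session comparisons at each time are affected. If the first visit adds c to the pre-session reading only, the change on that visit shifts by −c, so |π| = c.

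**6. Which term removes it.** A period main effect is constant over the five readings of a visit, so by step 5 it also drops out of every session × time contrast. At 14/7, with a 4 mmHg first-visit rise at the pre-session reading only, the 45-minute contrast is off by 1.33 mmHg without a period term and still by 1.33 mmHg with a period main effect. The error goes to 0 only with period × time, or with sequence-adjusted change scores.

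**The case against.** The strongest reply is that randomisation already protects the estimate: over repeated randomisation it is unbiased, and type I error averages about 5%. That stands. Bias exists only conditional on an uneven split, and near balance the test is conservative rather than liberal. What remains is that this trial has one realised split, fixed and unreported, and that the precision loss occurs even at 11/10.

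A second reply is that the hypothesis is tested by session × time, from which a uniform first-visit shift cancels. That also stands, and it narrows the point to shifts that vary within the visit. The documents offer no evidence that such a shift occurred. Anticipation specific to the class is not a period effect either, since it follows the class to whichever visit holds it.

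Third, a reader might infer from the odd sample size, or from the 34% chance of an 11/10 split, that the orders were in fact unbalanced. The documents do not support this. An 11/10 split leaks under 5% of any period effect, and the text is compatible with blocked or counterbalanced order. What can be shown is that the method and the split are not reported.

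**Conclusion.** The point holds in a limited form. The stated model omits the factor that the trial randomises. If the first visit changes the within-visit course of blood pressure, the session × time contrast loses precision near balance and is shifted in proportion to the imbalance otherwise. At an assumed SD of 8 mmHg, period effects of 1, 2, 3 and 4 mmHg inflate the variance at 11/10 by about 2%, 6%, 14% and 25%. A 4 mmHg effect gives a bias of 0.2 mmHg at 11/10, about 0.7 mmHg on average if simple randomisation was used, and 1.3 mmHg at 14/7.

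Every mmHg value here is an assumption; the documents supply neither a period effect nor an SD. It would be going too far to conclude that the trial's result is biased or its type I error inflated, because that needs both a time-varying period effect and an uneven split, and the documents show neither. The point calls for a modest correction to analysis and reporting. It does not invalidate the design.

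**What to change.** For SBP, compute each woman's change from the pre-session reading to each post-session time in each session. Take the pole-dance-minus-control difference in change, and regress it on sequence coded ±1/2. The intercept is then the order-adjusted session effect at that time. Equivalently, fit a mixed model with session, time, session × time, period and period × time; a period main effect alone is not enough.

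Report how the order was generated and how many women took each order. Keep the claim that random order secures balance only if the order was blocked or counterbalanced.

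The cost is 1 df per contrast and no new data: the Timeline says collection is complete, and each woman's order should be on record. In the mixed model it is 1 + 4 = 5 extra fixed-effect parameters over the five readings. With no period effect, the standard error rises by the factor 1/√(1 − (imbalance/21)²): 0.1% at 11/10, 3% at 13/8 and 6% at 14/7. In the simulation at SD 8 mmHg with a 5 mmHg session effect and no period effect, power went from 0.776 to 0.772 at 11/10 and from 0.776 to 0.725 at 14/7.

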### **Inclusion Criteria**

Participants were eligible if they were female, aged 18 years or older, had an intermediate level of pole dance experience (with the ability to perform aerial movements of medium difficulty, including inverted figures), and had not performed vigorous physical activity within the previous 24 hours.

### **Exclusion Criteria**

Participants were excluded if they were pregnant, if they presented injuries that limited the practice of pole dance, or if they had clinical conditions that contraindicated physical effort.

### **Procedures**

At the beginning of the study, participants underwent an anamnesis to collect sociodemographic data, lifestyle information, comorbidities, and details related to pole dance practice. Anthropometric measurements, including weight, height, and body mass index, were also recorded. In the experimental session, participants completed a 60-minute pole dance class, which included a 15-minute warm-up with joint mobility and stretching exercises, followed by 10 minutes of strength and resistance training combined with transitions. The next 15 minutes focused on aerial movements using the static pole, while another 15 minutes were dedicated to sequences on the spinning pole. The session concluded with a 5-minute passive stretching period. In the control session, participants remained seated for 60 minutes without performing any physical effort.

Blood pressure and heart rate were measured using a digital sphygmomanometer (Omron HEM-7113) at five time points: before the session, immediately after, and at 15, 30, and 45 minutes post-session. Participants were instructed to avoid caffeine, alcohol, smoking, and vigorous physical activity in the 24 hours prior to data collection. Perceived exertion was assessed at the end of the experimental session using the Borg modified scale (0–10).

### **Statistical Analysis Plan**

Data analysis was performed using SPSS version 17.0. Descriptive statistics were used to characterize the sample, with continuous variables expressed as mean and standard deviation, and categorical variables expressed as absolute and relative frequencies. Differences in systolic blood pressure, diastolic blood pressure, and heart rate between sessions and across time points were analyzed using repeated measures ANOVA (session  $\times$  time), followed by Bonferroni post-hoc tests. Spearman's correlation coefficient was applied to examine associations between blood pressure, heart rate, and perceived exertion. A significance level of  $p < 0.05$  was adopted for all analyses.

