### **Timeline**

The study was conducted and completed in 2023. Data collection occurred during that year, with each participant performing both the experimental and control sessions on separate days. Blood pressure and heart rate were monitored for 45 minutes after each session, and statistical analyses were finalized following data collection.

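### The planned repeated measures ANOVA normally needs all 10 readings per woman and outcome, so one failed reading would discard the rest of her data; a mixed model would keep them

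*Combined protocol and SAP*

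**What the plan says.** The Statistical Analysis Plan names one method for the three haemodynamic outcomes: "Differences in systolic blood pressure, diastolic blood pressure, and heart rate between sessions and across time points were analyzed using repeated measures ANOVA", in a session-by-time layout with Bonferroni post-hoc tests. On software it says only "Data analysis was performed using SPSS version 17.0"; the procedure within that package is not named.

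Study Design gives the sample size, "The sample consisted of 21 women practicing pole dance at an intermediate level", and the crossover structure, "Each participant performed two sessions on different days". Procedures schedules blood pressure and heart rate "at five time points: before the session, immediately after, and at 15, 30, and 45 minutes post-session". Timeline repeats the attendance statement: "with each participant performing both the experimental and control sessions on separate days".

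No section states an analysis set, a rule for missing or repeated readings, imputation or a mixed model. No section reports a missing reading either.

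**The concern.** A classical repeated measures ANOVA with two within-subject factors works on complete rows. A woman with nine of ten readings is treated as if she had none.

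The Introduction hypothesises a fall in systolic pressure, and Expected Results places it at 45 minutes. The documents do not define the contrast. Taken as the change from baseline to 45 minutes, pole dance minus control, it uses four of the ten readings. A failure at any of the other six would still remove the woman from a model that requires complete rows. The reading straight after an hour of exertion is a plausible place for an automatic cuff to fail.

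The stake is precision in a sample of 21. Recorded data would be thrown away when a standard alternative could use them. This goes beyond a missing policy statement, because the deletion follows from how the named method usually works.

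**Working it through.** The plan gives no power, effect size, standard deviation or missing-data rate, so there is no stated figure to reproduce. Missing rates and variances below are assumptions.

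**Inputs from the documents.** 21 women and 2 sessions (Study Design); 5 time points (Procedures); significance level 0.05 (Statistical Analysis Plan), taken here as two-sided because the plan does not say.

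**Step 1: readings needed.** 2 × 5 = 10 per woman per outcome; 21 × 10 = 210 in total per outcome.

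**Step 2: complete records, two patterns.** Let m be the chance that a reading is missing.
- Pattern A: only the immediate reading after the class can fail. Expected complete women = 21 × (1 − m).
- Pattern B: all ten readings fail independently. Expected complete women = 21 × (1 − m)^10.

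| m | Pattern A | Pattern B |
|---|---|---|
| 0% | 21 | 21 |
| 1% | 21 × 0.99 = 20.8 | 21 × 0.904 = 19.0 |
| 2% | 21 × 0.98 = 20.6 | 21 × 0.817 = 17.2 |
| 5% | 21 × 0.95 = 19.95 | 21 × 0.599 = 12.6 |

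Under pattern B at 2%, about 3.8 women are dropped (21 − 17.2), and with them about 34 readings that were taken: 210 × 0.98 − 210 × 0.817 = 205.8 − 171.6. Failures clustered in the same women would cost fewer women than pattern B.

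**Step 3: power with complete cases.** For a two-sided paired t test at 5%, the effect with 80% power at n = 21 is 0.643 standard deviations of the paired difference. Power at that effect is:
- n = 20: about 78% (pattern A at 5%)
- n = 19: 75.5% (pattern B at 1%)
- n = 17: 70.2% (pattern B at 2%)
- n = 13: 56.8% (pattern B at 5%)

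**Step 4: what a mixed model would recover.** The variance of the 45-minute contrast was found by generalised least squares with known covariance, over 400 simulated missingness patterns per setting. Two splits of person, session and residual variance were assumed (60/20/20 and 40/20/40); they agreed to two decimals except for the mixed model at 10% missing (1.145 and 1.141). Ratios are to full data under pattern B.

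| m | Complete cases | All readings, mixed model |
|---|---|---|
| 0% | 1.00 | 1.00 |
| 1% | 1.11 | 1.01 |
| 2% | 1.24 | 1.03 |
| 5% | 1.73 | 1.07 |

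Dividing 21 by the mixed-model ratio gives an effective sample: at 5%, 21 / 1.07 = 19.6, with power about 77%. At 1% and 2% power is about 79%.

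**Step 5: gain from changing method.** At 5% missing under pattern B, 77 − 57 = about 20 percentage points. At 1%, about 4 points. Under pattern A at 5%, at most 80 − 78 = about 2 points. If whole sessions are missed instead, the gain is small: with 10% of women missing one session the ratios are 1.12 for complete cases and 1.06 for the mixed model.

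**The case against.** The strongest reply is that nothing may have been lost. Every woman is said to have done both sessions, Procedures describes measurement at all five times, and Timeline says monitoring ran for 45 minutes after each. None of this establishes that each cuff reading succeeded, but no section suggests that one failed. With complete data the two methods agree on the contrast. This stands, and it makes the point conditional.

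Second, the most plausible failure is the reading straight after the class, one cell in ten. A calculation in which all ten cells fail at the same rate overstates the loss under that mechanism. This also stands, so the 13-woman figure is one end of a range and not an expected result.

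Third, complete-row deletion is inferred. Neither the SPSS procedure nor the computation of the Bonferroni comparisons is given. Separate paired comparisons would use every woman with the relevant readings, and a failed reading may have been repeated on the spot. This stands for the post-hoc tests. For the named session-by-time ANOVA, deletion remains the usual behaviour.

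A reader might go further and infer that the trial did discard data, or that its result is biased because women with failed readings respond differently. The documents support neither. They link no failure to response, and if failure depended on the unobserved value itself, a mixed model could be biased too.

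**Conclusion.** The point holds as a conditional weakness of the chosen method. If any reading is missing, the ANOVA as normally run drops that woman's other readings, including those at 45 minutes, and no stated rule offsets this. If none is missing, the contrast is essentially unchanged.

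The size is a range that depends on assumptions. At 5% missing, power for an effect with 80% power at n = 21 runs from about 78% under pattern A to about 57% under pattern B. The mixed-model figure of about 77% under pattern B assumes known covariance and the variance splits given above; with covariance estimated from 21 women the advantage is expected but not guaranteed. It would be wrong to read the plan as showing an actual loss of 8 women or 20 points of power.

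**What to change.** 1. Report, for each of systolic pressure, diastolic pressure and heart rate, how many of the 21 women have all 10 readings. This settles whether the issue affected the trial.
2. Analyse all available readings with a linear mixed model fitted by REML. Use fixed effects for session, time, session × time and period; random effects for participant and participant-by-session; time-specific residual variances; and Satterthwaite degrees of freedom. Take the 45-minute systolic contrast and its 95% confidence interval from this model. The period term and the interval are worthwhile in their own right but are not needed to answer the missing-reading point.
3. Timeline says the analyses were finalised, although the document is dated 2022 and the study is said to have run in 2023. If the ANOVA has already been run, label the mixed model as a post hoc re-analysis and show both results.

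The cost is revised SAP wording, one extra model run, and a covariance structure that must be stated for a sample of 21. No new data are needed.
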